1. INTRODUCTION

1.1. History of Cryotherapy

Cryotherapy (or cryoablation) is a safe, well-established FDA-cleared technology that has been successfully applied for selective ablation and treatment of different kinds of benign and malignant conditions, such as: prostate and renal cancer, liver lesions, soft tissue lesions, fibroadenoma of breast, ear-nose and throat applications, thoracic applications (atrial fibrillation, pulmonary lesions), cryoanalgesia, dermatology, as well as pre-cancerous lesions of the cervix. Galil Medical has developed a range of products based on its cryotherapy platform and incorporating updated freezing technology and needle design.

Applying cold energy to human tissues is a well-known technique for treating various tumors as an alternative to surgery.¹⁻¹¹The first modern physician to utilize this technique was James Arnott (England, 1865). Since Arnott's first experience, many trials have been conducted utilizing various techniques and devices.^{8,10}These have included pre-cooled metal blocks, pre-cooled needles, ^{11,12} dry ice applications, spray/pour freezing with compressed or liquefied gasses, ^{12,13} refrigeration systems, thermoelectric methods and cryogenic heat pipes, ¹⁴ cryogenic needles, ¹⁵ Joule-Thomson-effect-based cryoprobes, ^{15,16} and boiling-effect-based cryoprobes. ¹³ To increase the effectiveness of the cryo-treatment, the freezing protocols used by these physicians were adjusted with the known maximal cryo-destruction criteria such as extremely fast cooling, ⁹ low cooling rate at the freezing front, ¹⁹ slow thawing, ²⁰ and repeated freeze/thaw cycles. ¹⁴

As tissue temperatures fall, extracellular water begins to crystallize and a hyperosmotic extracellular environment is created that draws water out of the cells. As the process continues, extracellular ice crystals grow, cells shrink, and membranes and cell constituents are severely damaged. Within a short time (minutes), the increased extracellular electrolyte concentration is sufficient to destroy the cells. This effect of cell dehydration and solution concentration, called solution-effect injury, is not always lethal to cells; on the other hand, intracellular ice formation is a more significant threat to cell viability and is almost always lethal.8 Solution-effect injury is associated with low freezing rates, while intracellular ice formation is commonly associated with fast freezing rates. Although pure water begins to freeze at 0°C, extracellular ice formation occurs at approximately -7°C to -10°C, by -15°C intracellular ice begins to form (heterogeneous nucleation). Depending on the tissue characteristics (e.g., vascularity, density, etc.) at -20°C to -40°C all metabolic processes are expected to have ceased (homogenous nucleation). The most destructive effect on biological tissue is achieved by either an extremely low temperature or a very rapid freezing rate (on the order of hundreds of degrees Centigrade per minute). 8,9 More recent in vitro and in vivo work has identified apoptosis as the mechanism associated with direct cell injury. Cell death has been demonstrated in the central part of the ablation zone by evidence of coagulation, while apoptosis is evident generally 8-12 hours after cryoablation in the peripheral part of the lesion. 17

Cryoablation is an advantageous therapy as it preserves collagenous and other cellular architecture in virtually any frozen tissue and offers the ability to see low attenuating ice as it covers soft tissue 18

Modern cryoablation dates back to 1961, when automated cryosurgical units that pump liquid nitrogen through the tip of the cryoprobe were introduced. This innovation led to the investigation of cryoablation for different diseases, but cumbersome cryoprobes and a lack of control over the freezing process made widespread use impractical. The resurgence in interest in cryoablation results from the introduction of modern cryoprobes, which exploit the Joule—Thomson (J–T) effect. The J–T effect predicts changes in temperature as gases expand through narrow ports from high to low pressure. This is a constant enthalpy expansion that, in the case of argon gas, results in rapid cooling to the boiling point of argon (-186°C). To accomplish this, high-pressure (3,000 – 3,500 psi) ambient-temperature argon gas is circulated to the cryoablation needle tip where it expands rapidly as it drops to room pressure. Under the J–T effect, some gases - such as helium - warm up rather than cool when expanded.

CUC10-LNG06-04 Page 5 of 38

Accordingly, helium can and has been incorporated into cryogenic systems to rapidly warm the cryoablation needle in order to arrest the freezing process or thaw the iceball. The flow of argon and helium is controlled by computer-modulated gas regulators. The temperatures of cryoablation needles controlled by gas systems are finely adjustable and respond within seconds to user input. (By comparison, liquid nitrogen systems have a lag time of up to 2 min). The expanded gases are circulated back to the cryogenic unit through the larger outer lumen of the cryoablation needle and the supply hose. The venting of used gas, usually into the room, occurs at the cryogenic machine. Both argon and helium are inert gases, making such venting harmless

The cryoablation technology developed by Galil Medical, Ltd. (Yokneam, Israel) is based on Joule-Thomson effect, and utilizes Argon gas for freezing and Helium gas for thawing.

This study will utilize Galil Medical's commercially available Cryoablation System and needles. Each cryoablation needle forms a different shape and size of iceball. Multiple cryoablation needles may be inserted into the tumor, or even into 2 or 3 tumors concomitantly. This significantly shortens the length of treatment and provides flexibility in treating tumors of varying sizes by matching the cryoablation needle number and configuration for a specific tumor.

Tissue thermal sensors may be employed to enable the real-time tissue temperature monitoring, thus, contributing to the safety and effectiveness of the procedure.

Cryoablation procedures using Galil Medical's Cryoablation Systems may be performed under the guidance of Ultrasound, Computed Tomography (CT) or Magnetic Resonance Imaging (MRI).

1.1. Historical Background of Metastatic Lung Cancer

The first surgical resection of a pulmonary metastasis (sarcoma) dates back to 1882 and is credited to Weinlechner. Barney and Churchill performed the first isolated resection of a pulmonary metastasis in the United States in 1939. In the past 25 years, surgical resection has become widely accepted for the treatment of pulmonary metastases.²¹

Today, lung cancer is the most frequent malignancy causing death in the world. Common primary tumors that usually present as lung metastasis are breast, colon, kidney, uterus and cervix, prostate, and head and neck tumors. Though surgery, with or without systemic chemotherapy, remains the treatment option of choice, not all patients are considered appropriate candidates for this treatment option.²² Therefore, it is necessary to develop alternative, less invasive treatments for patients who are not candidates for surgery.

1.2. Metastatic Lung Cancer Treatment Options

The choice of treatment depends mainly on the type of lung cancer and its stage. Treatment may include surgery, chemotherapy, radiation therapy, targeted therapy, or a combination of treatments, depending on the stage and size of the tumor. Treatment may be local or systemic.²³

Surgery is typically the best option with localized disease (no mediastinal invasion), however only 25% of tumors are suitable at the time of diagnosis for potential curative resection. Chemotherapy and/or external beam radiation (XRT) with chemotherapy is generally the standard treatment for regional disease. If the primary malignancy is controlled and there is no evidence of extrathoracic disease, then resection may be considered. Besides the traditional treatment options, minimally invasive treatment options include stereotactic radiotherapy, brachytherapy, bronchial arterial infusion of chemotherapy, photodynamic therapy and thermal ablation. Ablative technologies that are emerging as treatment options for lung cancer tumors include radiofrequency, microwave and cryoablation. ²²

CUC10-LNG06-04 Page 6 of 38

2. DEVICE DESCRIPTION

Galil Medical's Cryoablation Systems (Galil Medical, Ltd, Yokneam, Israel) and needles are FDA cleared. The Galil Medical Cryoablation Systems are intended for cryogenic destruction of tissue during surgical procedures; various Galil Medical ancillary products are required to perform these procedures. Galil Medical Cryoablation Systems are indicated for use as a cryosurgical tool in the fields of general surgery, dermatology, neurology (including cryoanalgesia), thoracic surgery, ENT, gynecology, oncology, proctology and urology. These Systems are designed to destroy tissue (including prostate and kidney tissue, liver metastases, tumors, skin lesions and warts) by the application of extremely cold temperatures.

3. CLINICAL BACKGROUND

3.1. Cryoablation in the Treatment of Lung Tumors

Ablation of lung tumors is the fastest expanding area within interventional oncology. Radiofrequency, laser, microwave and cryotherapy have all been shown to be effective. 24 Cryotherapy has a wide range of anatomic and tumor treatment options because of the ability to visualize the ice under imaging guidance and the preservation of collagenous tissue structure. Additionally, only minor discomfort at the procedure site has been noted and this typically resolves within 48 hours of the procedure. Cryoablation has been performed in the prostate and kidney with favorable outcomes reported in the literature. More recently, cryoablation has been shown to be safe in the treatment of lung tumors with basic CT guidance. 25

3.2. Previous Clinical Studies Leading Up to and Supporting the Proposed Research

Asimakopoulos et al reported 5 year follow-up of a series of 172 patients (Group A) who underwent 2 cryoablation treatments and 157 patients (Group B) who underwent 1 cryoablation treatment for primary or metastatic obstructive lung disease. Subjects assigned to group A were able to complete the standard cryosurgery protocol and subjects in group B were those only able to undergo 1 session of cryoablation. The primary outcome was to examine the effects of cryosurgery on symptoms, lung function, and performance scores. Dyspnea was classified using the New York Health Association (NYHA) classification. Tumor stage at the time of cryoablation was determined to be stage IIIb or IV in 67% of group A and 77% in group B. Treatment was performed using a nitrous oxide cryoprobe (Spembly Medical, UK/Integra Life Sciences) which achieved a temperature of -70 C at the time of treatment. Treatment was applied to the tumor for two 3-minute freeze cycles. Ninety-five percent of the patients were discharged on the same day as the cryoablation procedure. Patients were scheduled for followup at 2 weeks and 8 weeks after the second session of cryotherapy. Complications reported after cryotherapy included bleeding in 3.5% of group A and 5% of group B, new onset of atrial fibrillation in 1.7% of group A and 3.8% of group B, and respiratory distress in 2.3% of group A and 5% in group B. Palliative or adjuvant treatment with radiotherapy, chemotherapy or resection was provided based on the tumor stage, histology, or patient preference. Squamous cell carcinoma was present in 66% of patients in group A and 63% of those in group B. Fifty seven percent of group A underwent palliative radiotherapy, 11% chemotherapy, and 7% resection. Twenty eight percent of group B underwent palliative radiotherapy, 11% chemotherapy, and 5% resection. Dyspnea improved by at least one NYHA classification in 37% of subjects in group A and only in 11% of those in group B by their second follow-up. Cough improved in 43% of group A and 11% in group B and hemoptysis in 20% of group A and 4% of group B. Data was limited in group B due to the limited follow-up attendance. Lung function also increased significantly in group A at their first follow-up but the benefit was lost by their second visit. Patients in group B did not show improved lung function by their first followup visit. The mean survival after cryotherapy was 15 months in group A and 8.3 months in group B. Karnofsky score improved at least 10% in group A as well as in group B. The clinical benefit of cryosurgery is primarily attributable to tumor debulking, achieved by the destruction of

CUC10-LNG06-04 Page 7 of 38

the endobronchial element of the tumor and recanalization of the tracheobronchial obstruction. The removal of this obstruction accounts for the improvement in dyspnea and lung function tests, which are vital to the alleviation of symptoms in those with lung cancer due to the poor prognosis of this disease.²⁶

Kawamura et al reported a series of 35 tumors in 20 patients treated with cryosurgery for metastatic pulmonary tumors. Criteria for treatment included tumors < 3cm, less than 5 metastatic tumors, life expectancy greater than 1 year, absence of active extrapulmonary metastasis, Eastern Cooperative Oncology Group scores of 0 to 1, definitive pathologic diagnosis or obvious clinical features, and normal coagulability. CT guided cryoablation was performed with a 2 or 3 mm diameter cryoprobe (Endocare, Inc.) with 2 cycles of 5 minute freezing followed by a third cycle of 10 minute freezing to make an iceball of 2.5 to 3.0 cm in diameter. Local anesthesia was used in all cases. The primary endpoint of this study was the early outcome and feasibility of cryoablation for metastatic tumors < 3 cm. The secondary endpoint was tumor control. The mean age of patients was 57 years old. Two of the 20 patients underwent cryoablation twice due to bilateral metastasis, resulting in a total of 22 cryosurgery sessions. Pneumothorax occurred in 11 of 22 treatment sessions. Seven cases of pleural effusion, 8 cases of hemoptysis, and 1 case of phrenic nerve palsy were reported. The mean hospital stay was 2.6 days.

There were no treatment related deaths or conversion to surgical intervention. Response Evaluation Criteria in Solid Tumors (RECIST) was applied to assess change in tumor mass post-operatively. Two patients had complete response, 8 had partial response, 8 had stable disease, and 2 had progressive disease, thus resulting in a 50% response rate. The overall tumor recurrence rate was 54.3%. The median follow-up was 21 months for 18 patients. During the 9-12 month period, 7 of the 18 patients developed a local recurrence of 7 (20%) of tumors in 7 (35%) patients. Five patients underwent additional cryosurgery without complication or local recurrence. Pneumothorax was reported in 50% of the cases, 27% experienced pleural effusion, 41% hemosputum, and 4.5% phrenic nerve palsy. The Kaplan Meier 1-year survival was 89.4%.²⁷

Wang et al reported a series of 187 patients who underwent CT guided percutaneous cryoablation for thoracic masses. The mean age of the patient population was 61 years. Primary lung cancer accounted for 84% of the tumors in 88% of the patients while metastasis was found in 12% of the patients. PCT procedures were performed with 2 and 3mm cryoprobes (Endocare). A treatment cycle consisted of a 20 minute freeze, 10 minute thaw or increase in temperatures to 0-5° C, followed by another 20 minute freeze. A single cryotherapy session was performed in 178 (76%) patients. Repeat ablations were performed for larger central masses, multiple pulmonary masses, and bilateral masses. There were no intra-operative complications or technical difficulties. CT images were obtained immediately after the cryoablation procedure. The ice was well seen, however it was not possible to visualize the frozen tissue in the adjacent lung, and therefore only estimates of ice coverage of soft-tissue components of thoracic masses could be made. Tumor size and location were significant variables for determining the likelihood of tumor coverage with ice. Peripheral masses < 4 cm had mean ice coverage in 99% of the cases and 80% coverage were noted for central masses > 4cm. Two deaths occurred after the cryosurgery. One patient died within 1 day due to a pulmonary embolus and the second a week after the procedure due to acute respiratory distress. Pneumothorax occurred on 12% of the procedures, pleural effusion in 14%, and hemoptysis 62%. The Karnofsky score improved significantly one week after the procedure. CT imaging after the cryoablation procedure was performed at 1 week, 3 month, 6 months and 12 months when possible. Larger areas of cavitation were noted at the 1 week interval, however areas nearly resolved by 3 months with only 7% of masses still showing cavitation. Cavitation was noted to be a good indicator of thorough tumor ablation coverage and emphasized the need for 1-cm ablative margins as treatment goals. By 6 months, 86% of the cases demonstrated involution or stability of the treatment site. Due to low follow-up, the calculation of accurate survival estimates was not possible. 28

CUC10-LNG06-04 Page 8 of 38

3.3. Rationale Behind the Proposed Research

Less than 25% of patients diagnosed with lung cancer have localized disease and are surgical candidates. There are many different methods of for treating pulmonary metastatic disease. Surgery is typically used when the disease is localized and chemotherapy with or without XRT is used when the disease is regional. However, several variables may exclude patients from these treatments.

The target population for this study is patients with pulmonary metastatic disease who are candidates for cryoablation therapy. This study will evaluate the safety and efficacy of cryoablation therapy used to treat tumors in patients with pulmonary metastatic disease.

4. STUDY OBJECTIVE

4.1. Study Objective

The objective of this study is to assess the feasibility of cryoablation in local tumor control for tumors ≤3.5 cm in patients with pulmonary metastatic disease.

5. STUDY DESIGN

This is a Phase 1 multicenter, prospective, single arm study with patients serving as their own control. This study is to enroll at least 30, but up to 40, patients who will undergo cryoablation of at least 1 metastatic pulmonary tumor via a Galil Medical cryoablation system using Galil Medical cryoablation needles.

Patients will be screened within 6 weeks of the cryoablation procedure. After the cryoablation procedure visit date, follow-up visits will consist of within 1 Week of the cryoablation procedure and then 1, 3, 6, 12, 24, 36, 48 and 60 months post cryoablation procedure.

5.1. Efficacy Endpoints

The efficacy endpoint for this study is defined as follows:

 Assessing the effectiveness of cryoablation on local tumor control in patients with pulmonary metastatic disease at 3, 6, 12, 24, 36, 48 and 60 months post cryoablation.

5.2. Safety Endpoints

The safety endpoint for this study is to assess the incidence and severity of cryoablation related adverse events.

5.3. Other Endpoints

Other endpoints for this study include, but are not limited to:

- Assessing overall disease specific survival at 3, 6, 12, 24, 36, 48 and 60 months post cryoablation.
- Assessing time to disease recurrence or progression.
- Assessing the changes in physical function and quality of life over time. (See Section 11.5.4)
- Assessing cryoablation technical success. (See Section 11.5.4)

5.4. Tumor Characteristics

Tumor characteristics will be recorded at baseline.

5.4.1. Characteristics

Tumor characteristics will include, but are not limited to:

CUC10-LNG06-04 Page 9 of 38

- Histology of primary tumor;
- Proof of metastases
- Location of the tumor(s) in the lung(s);
- Size of the tumor(s);
- Number of tumors.

5.5. Physical Function

Physical function is considered routine clinical practice in medicine. Specifically, in oncology practice, physical function assessments such as the Eastern Cooperative Oncology Group (ECOG) and Karnofsky Performance Scale (KPS) have been incorporated.

This study will use ECOG and KPS to assess physical function.

5.6. Quality of Life

Oncology trial outcome measures appropriately focus on physical response to therapy and severe adverse events. However, over the past two decades, trial measurement has increasingly included the impact of therapy on the broader arena of quality of life, defined by a number of physical and psychosocial domains.^{29,30}The underlying concept is that quality of life may assist in distinguishing treatments that are otherwise similar in therapeutic value and toxicity. There has been some debate about the clinical usefulness of quality of life measures, but at least one recent report has documented their impact on clinical decision-making.³¹

This protocol will utilize the SF-12 generic measure. The SF-12 is a shortened version of the well-known SF-36. The SF-12 uses twelve items to assess eight domains (physical functioning, role limitations due to physical health problems, bodily pain, social functioning, general mental health, role limitations due to emotional problems, vitality, general health perception).³² The shorter instrument was selected because it will reduce participant burden yet still give a general measure of quality of life.

6. STUDY TREATMENTS

6.1. Treatment

For cryoablation, patient preparation, anesthesia, intra-operative monitoring, and post operative management are identical to those of standard cryoablation treatments routinely performed at all clinical centers participating in this study and are at the discretion of the investigator.

6.2. Additional Treatment

Patients may not receive additional local treatment to the index tumor(s) subjected to cryoablation while participating in the study protocol. If additional local treatment (e.g. ablation, surgery, radiation) is required, then the patient must be withdrawn from the study.

Data will be collected on any additional systemic cancer therapy the patients receive during the course of the study.

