6.4. Patient Withdrawal

Patients may withdraw from this study at any time, with or without a reason, without prejudice to further treatment. Investigators should make every effort within the bounds of safety and patient choice to have each patient complete the study. If a patient does not return for a scheduled visit, every effort should be made to contact the patient. In any circumstance, every effort should be made to document patient outcome, if possible. The investigator should inquire about the reason for withdrawal; request the patient return for a final visit, if applicable and follow-up with the patient regarding any unresolved adverse events. As possible, the reason(s) for withdrawal (if given) will be recorded.

If the patient withdraws from the study and also withdraws consent for disclosure of future information, no further evaluations should be performed and no additional data should be collected. The sponsor may retain and continue to use any data collected before such withdrawal of consent.

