8.6. Months 24, 36, 48, 60 and Study Completion or Withdrawal

Patients will return 24, 36, 48 and 60 months (+/- 90 days) post cryoablation procedure or at Study Withdrawal and complete the following assessments:

- ECOG;
- Karnofsky Performance Scale;
- Quality of Life assessments (SF-12);
- CT/MRI Scan, with contrast:
- Safety assessments;
- Assessment of disease progression, including retreatment;
- Assess any new cancer treatment(s).

Patients who request Early Termination from the study will be asked to return for a final visit to complete the above assessments.

Patients may be considered "lost to follow-up" after 3 unsuccessful attempts to contact the patient with on contact being a registered letter to the last known address of the patient. Site should document all attempts to contact the patient in the source documents.

CUC10-LNG06-04 Page 16 of 38

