#### Imaging and lung function

- Number of tumors
- Number of new tumors (at follow-up)
- Number of tumors treated with cryoablation (at baseline)
- Number of tumors not treated with cryoablation (at baseline)
- Tumor response (per tumor)
- Tumor distribution
- Location (per tumor)
- Greatest trans-axial diameter (per tumor)
- FVC (observed)
- FEV1 (observed, predicted and % predicted)
- DLCO/VA

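### Retreating one index tumor withdraws the whole patient, which ends scheduled follow-up of the other treated tumors, function, quality of life and survival, and removes the patient from later local-control rates

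*Protocol*

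**What the plan says.** Protocol 6.2 prohibits further local therapy to a treated tumor during the study: "Patients may not receive additional local treatment to the index tumor(s) subjected to cryoablation while participating in the study protocol". The consequence applies to the patient: "If additional local treatment (e.g. ablation, surgery, radiation) is required, then the patient must be withdrawn from the study". New systemic therapy, by contrast, is only recorded.

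Protocol 8.6 and Table 1 attach one set of assessments to withdrawal (imaging, SF-12, ECOG, KPS, safety, progression, new treatments): "post cryoablation procedure or at Study Withdrawal and complete the following assessments". Nothing is scheduled after that. Section 6.4 adds follow-up of unresolved adverse events and a general request: "In any circumstance, every effort should be made to document patient outcome, if possible". It stops data collection only when the patient also withdraws consent for disclosure of future information.

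Inclusion criterion 7.2.4 allows up to five pulmonary tumors. Protocol 11.5.2 and the SAP efficacy methods report local control per tumor and per patient, with the patients completing each visit as denominator. Local failure is growth in diameter of about 20% (protocol 9.7.5, SAP efficacy definitions); retreatment does not count as failure. Disease-specific survival to 60 months is listed in 5.3, as is "Assessing the changes in physical function and quality of life over time". Living patients are censored at their last visit in the survival analyses.

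**The concern.** A decision about one tumor ends scheduled observation of everything else in that patient. Three things are at stake.

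- **Other treated tumors.** Their scheduled imaging stops, although control is to be reported per tumor.
- **Function, quality of life and survival.** SF-12, ECOG, KPS and survival contact lose their schedule, even if the patient would keep attending. Survival censoring then depends on a clinical event after treatment and may be informative.
- **The local-control rate itself.** A patient retreated for local failure can count as a failure at most up to the withdrawal visit. At later visits the patient is in neither numerator nor denominator. A tumor retreated before reaching the growth threshold is never counted as a failure. Both features push later rates upward.

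Protocol 11.2 says the study's estimates will be used to power a pivotal study, so an inflated control rate could carry forward.

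**Working it through.** The documents give no figure for this rule, so there is none to reproduce. The steps below count what is lost and then illustrate the effect on the rates.

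**1. Time points lost per affected patient (Table 1; protocol 9.4 to 9.6).** Follow-up imaging: Months 3, 6, 12, 24, 36, 48, 60 (7). SF-12: Month 1 plus those (8). ECOG/KPS: Week 1 plus those (8, or 9 if Month 1 is a clinic visit).

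- Withdrawn after Month 12: at most 4 of 7 imaging, 4 of 8 SF-12, 4 of 8 ECOG/KPS.
- Withdrawn after Month 3: at most 6 of 7, 6 of 8, 6 of 8.

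The withdrawal visit gives back one set. Some patients would have died before the later visits. Assume a constant hazard from the 89.4% one-year survival of the cited 20-patient series (protocol 3.2): h = -ln(0.894) = 0.112 per year. Expected later visits reached = sum of exp(-h × HR × t), where HR is the withdrawn patient's hazard ratio.

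- From Month 12 (t = 1, 2, 3, 4), HR 1: 0.894 + 0.799 + 0.715 + 0.639 = 3.05. HR 2: 2.36. HR 3: 1.85.
- From Month 3 (t = 0.25, 0.75, 1.75, 2.75, 3.75, 4.75): 4.69, 3.78 and 3.13.

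**2. How many patients.** Unknown. For illustration, the same series reports "During the 9-12 month period, 7 of the 18 patients developed a local recurrence of 7 (20%) of tumors in 7 (35%) patients" and "Five patients underwent additional cryosurgery without complication or local recurrence". That is 7/20 = 35% with recurrence and 5/20 = 25% with further cryosurgery (not stated to be of treated tumors). Applied here: 0.25 × 30 = 7.5 to 0.35 × 40 = 14 patients. Neither rate is a bound, because surgery and radiation also trigger 6.2 and not every recurrence is retreated. At that series' 35/20 = 1.75 tumors per patient, with one recurrent tumor each, about 0.75 other tumors per affected patient would lose scheduled imaging: 7.5 × 0.75 = 5.6 to 14 × 0.75 = 10.5 tumors. The protocol maximum is 4 others per patient.

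**3. Effect on the patient-level control rate.** Assume 40 patients, 35% local failure (14), all withdrawals among failures, and everyone else attending. True control is 26/40 = 65%.

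| Withdrawn | Completer rate | Exact 95% CI |
|---|---|---|
| 4 (10%) | 26/36 = 72% | 55 to 86% |
| 10 (25%) | 26/30 = 87% | 69 to 96% |
| 14 (35%) | 26/26 = 100% | 87 to 100% |

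**4. Effect on 5-year survival.** Let f be the share of Month-12 survivors withdrawn at Month 12 (25 or 35%), r the share of them whose outcome is fully recovered under 6.4, and HR 0.5 to 3.

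- True S(5) = 0.894[f e^(-4hHR) + (1-f) e^(-4h)]
- Kaplan-Meier = 0.894[f r e^(-4hHR) + (1-f) e^(-4h)] / (f r + 1 - f)

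| Recovery | Error, f = 25% (points) | Error, f = 35% (points) |
|---|---|---|
| None (r = 0) | -3.6 to +8.5 | -5.0 to +11.8 |
| Random half (r = 0.5) | -1.5 to +3.6 | -2.0 to +4.7 |
| All | 0 | 0 |
| Every death found, living censored at Month 12 (numerical integration) | -7.2 to -2.8 | -10.6 to -4.4 |

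The 95% sampling half-width at S(5) = 0.894^5 = 0.571 is 1.96 √(0.571 × 0.429 / n) = 17.7 points (n = 30) or 15.3 (n = 40). Every error above is smaller.

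**The case against.** The best defense is that little is actually forbidden. A patient withdrawn under 6.2 has not withdrawn consent for disclosure, so 6.4 still permits collection and asks for it. Table 1 describes follow-up scans as routine, so they may exist anyway, and protocol 11.3 uses available dropout data. This stands in part: the loss is of scheduled data, not all data, and a reader who inferred that 6.2 bars survival follow-up would be going beyond the text. But best effort has no timetable and names no outcome, and it cannot replace SF-12, ECOG or KPS. Partial recovery can also distort, as the last row of step 4 shows.

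Second, the study is descriptive, and survival, function and quality of life are listed only among its other endpoints. That stands and limits the severity.

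Third, surgery or radiation for one tumor may reach a neighbor, so later control of the neighbor is not cleanly due to cryoablation. That stands and shapes the fix. It does not justify stopping function and survival follow-up, since 6.2 itself retains patients who start new systemic therapy.

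Fourth, the illustrative rates come from one small series using another manufacturer's probes, and the 5-year figures extrapolate a one-year estimate. Both are true; the figures show scale and are not forecasts.

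A reader might also infer that safety is compromised. It is little affected, because protocol 14 records only adverse events arising within 30 days of the procedure.

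**Conclusion.** The concern holds as a minor design point. As written, one retreated tumor ends scheduled imaging of the patient's other treated tumors and scheduled SF-12, ECOG, KPS and survival contact, leaving only unscheduled best effort. It also removes the patient from later local-control rates, which can bias them upward.

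Per affected patient, up to 4 of 7 imaging time points are lost after Month 12, or 6 of 7 after Month 3. How many patients are affected cannot be derived from the documents. The shift from 65% to 87% rests on an assumed 35% failure rate, on 25% of patients being withdrawn, and on all of those being failures; it should not be read as the expected bias. Nor do the documents support a claim that survival will be materially biased in a known direction: the sign depends on the hazard of withdrawn patients and on what 6.4 recovers, and in every scenario examined the error is below sampling error.

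**What to change.** **Follow-up.** Amend 6.2, and align 6.8, so that additional local treatment ends size assessment only of the retreated tumor and of any other index tumor inside the resection, ablation or radiation field. Keep the patient on the existing visits for the remaining index tumors, survival, SF-12, ECOG, KPS and safety unless consent is withdrawn. Retained patients then have current last visits, so the survival censoring rule need not change. Whether and how to retreat stays with the treating physician.

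**Local control.** In 9.7 and the SAP efficacy definitions, count the retreated tumor, and that patient at patient level, as not in local control from the retreatment date, and keep both in the denominator at later visits the patient attends. Do not score an untargeted in-field tumor as a response after that date. Assess the remaining tumors individually by the SAP per-tumor criteria.

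**Recording.** In 8.5 and 8.6, where retreatment is already an assessment item, add the tumor (index or not), date and modality. Flag later imaging of the remaining tumors and later SF-12, ECOG and KPS data, and summarize with and without the flagged records.

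**Cost.** An IRB-approved amendment, a consent-form revision if its withdrawal wording must change (the form is not among the documents), a few eCRF items and short SAP edits. No visits or procedures are added. The control rate may be slightly less favorable, because a tumor retreated below the growth threshold counts as not controlled, and later function and quality-of-life data will include the effect of the second treatment.
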